10.8 Multicenter Studies

This is multicenter study, with approximately 30 qualified investigator sites participating. Approximately 120 subjects will be randomly assigned, leading to approximately 4 subjects per site.

The expected low number of subjects at some sites does not allow for the site to be included as a covariate in the statistical model.

## 11. METHODS OF EFFICACY ANALYSIS

### 11.1 Montreal Cognitive Assessment Scale (MoCA)

The primary efficacy comparison will test the following hypotheses:

- $H_0$ : The change from baseline in MoCA score at Month 6 is equal when comparing both active treatment groups (combined) versus Placebo.
- $H_1$ : The change from baseline in MoCA score at Month 6 is different when comparing both active treatment groups (combined) versus Placebo.

Baseline and both observed values and change from baseline values for Day 28, Month 3, and Month 6 will be summarized by treatment group using descriptive statistics.

The difference between treatment groups (combined CT1812 vs. placebo) will be assessed using a mixed model for repeated measures (MMRM) with change from baseline values at Day 28, Month 3, and Month 6 as the response values, treatment group (CT1812 100 mg, CT1812 300 mg, placebo), time point, and a treatment group by time point interaction as fixed effects, subject as a random effect, and baseline value as a covariate. An unstructured covariance structure will be applied, and the denominator degrees of freedom will be computed using the Kenward-Roger method. If the model does not converge using the unstructured covariance structure, the autoregressive (order 1) AR(1) structure will be used. If the AR(1) structure also does not converge, other covariance structures deemed appropriate to fit the data will be used. The least square means (LSM), standard errors, LSM differences between combined CT1812 and placebo, 95% CIs for the LSM differences, and p-values at each post-Baseline time point will be presented.

The pairwise comparisons of each CT1812 group and placebo will be performed from the same model in a similar manner to what is described above.

Plots of mean MoCA score change from baseline with standard deviation over time, plots of LS mean MoCA score (from MMRM model) change from baseline with 95% CI over time, and spaghetti plots of individual subject MoCA score change from baseline over time will be provided. These three plots will be repeated using the completers/compliers population.

Subgroup analysis will be done for MoCA scores using subgroups defined in Section 10.6.

A listing for individual MoCA scores will be presented.

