14.4.3 Efficacy Analyses

Continuous efficacy endpoints will be summarized by treatment group and time-point using descriptive statistics as both absolute values and change from baseline. Differences between treatment groups will be assessed using a mixed model for repeated measures (MMRM) with treatment group, time-point, and a treatment group by time-point interaction as fixed effects, subject as a random effect, and baseline value as a covariate. The difference between the combined CT1812 group versus placebo at each time-point will be estimated based on the least square means (LSM) from the MMRM. The pairwise comparisons of each CT1812 group and placebo will be created in a similar manner.

Each efficacy endpoint will be listed.

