10.7 Multiple Comparison/Multiplicity

Although the assessment of efficacy is considered a secondary objective of this study, the key efficacy endpoint is defined as the change from baseline in MoCA score at 6 months. The primary analysis of this key efficacy endpoint will be based on the comparison of both CT1812 treatment groups combined vs. placebo. If the result of this analysis is statistically significant ( $p < 0.05$ ), then formal statistical testing will proceed as follows in a sequential manner:

1. CT1812 300mg/day vs. placebo
2. CT1812 100mg/day vs. placebo

If the comparison of CT1812 300mg/day vs. placebo is statistically significant ( $p < 0.05$ ) then the comparison of CT1812 100mg/day vs. placebo will be formally tested. If the comparison of CT1812 300mg/day vs. placebo is not statistically significant ( $p \geq 0.05$ ) then the result of the analysis of CT1812 100mg/day vs. placebo will be interpreted descriptively.

No adjustments for multiplicity will be made for the testing of the other endpoints evaluated in this study.

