### 11.2 Epworth Sleepiness Scale (ESS)

The ESS total score will be analyzed as described in Section 11.1. Plots of mean ESS total score change from baseline with standard deviation over time, plots of LS mean ESS total score (from MMRM model) change from baseline with 95% CI over time, and spaghetti plots of individual

subject ESS total score change from baseline over time will be provided for the ITT population only. A listing for individual ESS scores will be presented.

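### The MoCA repeated-measures model includes a redundant random subject effect, and its only named fallback forces equal variance at all visits, which makes the Month 6 standard error too small if that fallback is used and variance rises over time

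*SAP*

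**What the plan says.** SAP 11.1 fits a mixed model for repeated measures "with change from baseline values at Day 28, Month 3, and Month 6 as the response values". Fixed effects are treatment group, time point and their interaction. The specification continues: "subject as a random effect, and baseline value as a covariate. An unstructured covariance structure will be applied". It adds that "the denominator degrees of freedom will be computed using the Kenward-Roger method". It does not say whether the unstructured matrix is the residual covariance or replaces the random effect.

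The fallback has two steps. First: "If the model does not converge using the unstructured covariance structure, the autoregressive (order 1) AR(1) structure will be used". Then: "If the AR(1) structure also does not converge, other covariance structures deemed appropriate to fit the data will be used". No structure with visit-specific variances is named after the unstructured one, and no robust standard error is mentioned.

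SAP 10.7 states that "the key efficacy endpoint is defined as the change from baseline in MoCA score at 6 months". It tests combined CT1812 against placebo, then 300 mg, then 100 mg. SAP 11.1 takes all three comparisons from the same model. Other scales inherit that model; for example, "The ESS total score will be analyzed as described in Section 11.1". CAF, ADCS-ADL, MDS-UPDRS Part III, CDR and NPI do the same, and CGIC uses a similar model on observed scores.

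Protocol 14.4.3 has "subject as a random effect, and baseline value as a covariate" and names no residual covariance. The plasma biomarker model in SAP 13.2 also has a random subject effect and no stated covariance.

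**The concern.** Two weaknesses meet in one paragraph of SAP 11.1. A random subject effect on top of an unstructured matrix over-parameterises the covariance. The listed remedy for non-convergence is a structure with a single variance for every visit. A numerical difficulty created by the wording could therefore move the key analysis from a structure that protects the Month 6 standard error to one that does not.

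Kenward-Roger does not repair this: it makes a small-sample adjustment within the fitted covariance structure and does not correct a wrong one. The last fallback step is an open choice, although SAP 6 describes the analyses as defined before the blind is broken. What is at stake is the 5% level of each test in the MoCA hierarchy, and the standard errors of the scales that borrow the model.

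**Working it through.** **Inputs.** Three response visits (SAP 11.1) on Days 28, 98 and 182 (SAP 7). Two-sided 5% level (SAP 6). SD of change 1.32, difference 0.78, 105 evaluable and 120 randomized 1:1:1 (SAP 5, Protocol 14.2). The 105 evaluable are split 35 placebo and 70 combined active. SDs by visit are not given, so those at Day 28 and Month 3 below are assumptions.

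**Step 1: the plan's own figure.** SE = 1.32 × √(1/35 + 1/70) = 1.32 × 0.2070 = 0.273. Normal-approximation power = Φ(0.78/0.273 − 1.96) = Φ(0.894) = 81.4%; with the noncentral t it is 80.7%. The stated 80% is reproduced. The move from 105 to 120 implies 15/120 = 12.5% dropout. This point does not affect the sample size.

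**Step 2: parameter count.** An unstructured 3 × 3 matrix has 3 × 4/2 = 6 parameters; a subject variance makes 7. The total covariance is Σ = τ²J + R, where J is the matrix of ones and R is unstructured. For any admissible τ², R = Σ − τ²J gives the same Σ, so τ² is free. A numerical rank check agrees: 7 parameters, rank 6. Σ itself is still determined, and the contrast and its standard error depend only on Σ. AR(1) alone (2 parameters, rank 2) and AR(1) plus a random subject effect (3, rank 3) are identified.

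**Step 3: does the redundancy spoil the contrast?** In 60 simulated data sets (120 subjects, about 12.5% dropout, correlation 0.6, assumed SDs 1.00/1.15/1.32), REML fits with and without the extra term all converged. Month 6 estimates and standard errors agreed to within 0.00001. This was a quasi-Newton fit in Python without Kenward-Roger; SAS may behave differently.

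**Step 4: size of the error if AR(1) is used.** AR(1) has one variance, close to the average over visits. With complete data:

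- pooled SD = √[(s₁² + s₂² + s₃²)/3]
- model SE ≈ pooled SD × 0.2070, against a true 0.273
- actual level ≈ 2[1 − Φ(1.96 × pooled SD/1.32)]

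For 1.10/1.20/1.32: √[(1.2100 + 1.4400 + 1.7424)/3] = 1.210; ratio 0.917; 1.96 × 0.917 = 1.797; level 7.2%.

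| Assumed SDs, Day 28 / Month 3 / Month 6 | Pooled SD | AR(1) SE at Month 6 | Actual level |
|---|---|---|---|
| 1.50 / 1.40 / 1.32 | 1.409 | 0.292 | 3.6% |
| 1.32 / 1.32 / 1.32 | 1.320 | 0.273 | 5.0% |
| 1.20 / 1.26 / 1.32 | 1.261 | 0.261 | 6.1% |
| 1.10 / 1.20 / 1.32 | 1.210 | 0.251 | 7.2% |
| 0.90 / 1.10 / 1.32 | 1.120 | 0.232 | 9.6% |

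A large-sample likelihood fit of AR(1) gives nearly the same ratios (for example 0.849 to 0.850 against 0.848 in the last row). The group sizes cancel from the ratio, so the approximation is the same for each of the three comparisons. Keeping the random effect with AR(1) does not help, because the total variance is still constant over visits.

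**Step 5: simulation.** 1,500 REML fits per scenario under the null, 40 per arm, about 12.5% monotone dropout, correlation 0.6, model-based standard errors with fixed degrees of freedom:

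- 1.10/1.20/1.32: mean AR(1) SE 0.248 against an empirical 0.269; level 7.3% (7.5% with the random effect kept).
- 0.90/1.10/1.32: 0.229 against 0.269; level 9.7%.
- Equal SDs: level 5.3%.
- Unstructured without the random effect: mean SE 0.270 against 0.268 to 0.269; level 4.6% to 5.1% in all three scenarios.

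The Monte Carlo standard error at 7.3% is √(0.073 × 0.927/1500) = 0.7 points, so the 95% margin is about 1.3 points.

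**The case against.** The strongest reply is that the harm needs two conditions, and the documents establish neither. AR(1) applies only if the unstructured model fails to converge; redundancy alone did not cause that in Step 3, and a singular-Hessian warning is not the stated trigger. The standard error is understated only if the Month 6 variance exceeds the average over visits. The documents give one SD, and they describe cognitive fluctuation as a core feature of DLB, which could keep variance nearly constant. The random-effect phrase may also be loose wording for the subject as the repeated-measures unit. And safety is the primary objective, with efficacy secondary.

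All of this stands as a limit on size. It does not remove the point: the text literally names both components, the only named fallback drops visit-specific variances, and the step after it is open. If the phrase is shorthand, one sentence settles it.

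A reader might also infer that the biomarker model and Protocol 14.4.3 are non-identifiable. They are not, because neither names an unstructured matrix. Read literally with independent residuals, each implies compound symmetry. That is identified, but it forces equal variance across visits with no convergence failure needed.

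The unequal visit gaps (98 − 28 = 70 and 182 − 98 = 84 days) are a lesser mismatch with AR(1), and no effect of them was quantified.

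**Conclusion.** SAP 11.1 is wrong as written and should be corrected, but the consequence is conditional. The subject variance is redundant: 7 parameters for 6 quantities, which needs no assumption about the data. If the fallback is used and variance rises over time, the nominal 5% level becomes 6.1%, 7.2% or 9.6% under the three assumed rising patterns. It stays at 5.0% with equal SDs and falls to 3.6% with the falling pattern. These figures fix the Month 6 SD at the planned 1.32 and assume the earlier SDs.

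Two stronger readings are tempting and are not supported. One is that the Month 6 test cannot be estimated or is invalid: the contrast and its standard error remain identified if the software handles the redundancy. The other is that the trial's type I error is 7% to 10%: that ignores both conditions, and nothing in the documents gives the probability of the fallback or the SD by visit.

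The exposure covers all three hierarchical MoCA tests and the efficacy scales that refer to Section 11.1.

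**What to change.** - In SAP 11.1, delete the random subject effect. State that the unstructured matrix is the within-subject residual covariance, with Kenward-Roger degrees of freedom.
- Replace AR(1) and the open final step with a fixed order that keeps visit-specific variances: for example heterogeneous Toeplitz, then heterogeneous AR(1) or heterogeneous compound symmetry. Require robust standard errors if a homogeneous structure is ever used. The exact order is a matter of choice; fixing it before unblinding is what matters.
- Use the same specification in SAP 13.2, and list the difference from Protocol 14.4.3 in SAP 16.
- A baseline-by-visit interaction is optional; no bias from its absence was shown.

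The cost is SAP wording and slightly simpler code. Sample size and data collection do not change.

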### 11.2 Epworth Sleepiness Scale (ESS)

The ESS total score will be analyzed as described in Section 11.1. Plots of mean ESS total score change from baseline with standard deviation over time, plots of LS mean ESS total score (from MMRM model) change from baseline with 95% CI over time, and spaghetti plots of individual

subject ESS total score change from baseline over time will be provided for the ITT population only. A listing for individual ESS scores will be presented.

### 11.3 Clinician Assessment of Fluctuation (CAF)

The CAF severity score will be analyzed as described in Section 11.1. Plots of mean CAF severity score change from baseline with standard deviation over time, plots of LS mean CAF severity score (from MMRM model) change from baseline with 95% CI over time, and spaghetti plots of individual subject CAF severity score change from baseline over time will be provided for the ITT population only. A listing for individual CAF scores will be presented.

### 11.4 ADCS-Clinical Global Impression of Change (CGIC)

The CGIC outcome will be summarized for each treatment by time point (Day 28, Month 3 and Month 6). The summary will present the number and percentage of subjects in each outcome. Additionally, the continuous score, derived using the numeric score of each outcome response, will be summarized at each visit using descriptive statistics. Statistical modeling will be performed using an MMRM model similar to what is described in Section 11.1 but with the observed ADCS-CGIC values at Day 28, Month 3, and Month 6 as the response values.

The proportion of subjects classified as CGIC responders and non-responders will be summarized at each visit by treatment group.

Plots of mean ADCS-CGIC score change from baseline with standard deviation over time, plots of LS mean ADCS-CGIC score (from MMRM model) change from baseline with 95% CI over time, and spaghetti plots of individual subject ADCS-CGIC score change from baseline over time will be provided for the ITT population only.

Subgroup analysis will be done for the continuous ADCS-CGIC score using subgroups defined in Section 10.6.

A listing for individual ADCS-CGIC outcomes will be presented.

### 11.5 ADCS-Activities of Daily Living (ADCS-ADL)

The ADCS-ADL total score will be analyzed as described in Section 11.1. Plots of mean ADCS-ADL total score change from baseline with standard deviation over time, plots of LS mean ADCS-ADL total score (from MMRM model) change from baseline with 95% CI over time, and spaghetti plots of individual subject ADCS-ADL total score change from baseline over time will be provided for the ITT population only.

Subgroup analysis will be done for ADCS-ADL total score using subgroups defined in Section 10.6. A listing for individual ADCS-ADL scores will be presented.

## 11.6 Movement Disorder Society – United Parkinson’s Disease Rating Scale Part III (MDS-UPDRS Part III)

The MDS-UPDRS Part III total score will be analyzed as described in Section 11.1. Plots of mean MDS-UPDRS Part III total score change from baseline with standard deviation over time, plots of LS mean MDS-UPDRS Part III total score (from MMRM model) change from baseline with 95% CI over time, and spaghetti plots of individual subject MDS-UPDRS Part III total score change from baseline over time will be provided for the ITT population only. A listing for individual MDS-UPDRS Part III scores will be presented.

## 11.7 Cognitive Drug Research Battery (CDR)

The CDR composite scores will be analyzed as described in Section 11.1. The descriptive summary will be performed for each of the individual task measures. The descriptive summary and analysis will be performed for each of the composite scores (Power of Attention, Continuity of Attention, Cognitive Reaction Time, Response Variability, Quality of Working Memory, Quality of Episodic Secondary Memory, Speed of Memory, Quality of Memory). The calculation of composite scores is described in Appendix D.

Plots of mean CDR composite scores change from baseline with standard deviation over time, plots of LS mean CDR composite scores (from MMRM model) change from baseline with 95% CI over time, and spaghetti plots of individual subject CDR composite scores change from baseline over time will be provided for the ITT population only.

A listing for each individual task measures and composite score in CDR will be presented.

## 11.8 Neuropsychiatric Inventory (NPI)

The total NPI score for all domains (Total Score A-L), the total NPI score excluding Sleep and Appetite and eating disorders (Total Score A-J), the total distress score (Total Distress Score A-L), and the total distress score excluding Sleep and Appetite and eating disorders (Total Distress Score A-J) will be analyzed similarly as described in Section 11.1. The descriptive summary and statistical testing will also be performed for each of the 12 domain scores (Delusions, Hallucinations, Agitation/Aggression, Depression/Dysphoria, Anxiety, Elation/Euphoria, Apathy/Indifference, Disinhibition, Irritability/Lability, Aberrant Motor Behavior, Sleep, and Appetite and eating disorders), and for the caregiver distress scores for each of the 12 domains.

The total NPI score for all domains (Total Score A-L), the total NPI score excluding Sleep and Appetite and eating disorders (Total Score A-J), the total distress score (Total Distress Score A-L), and the total distress score excluding Sleep and Appetite and eating disorders (Total Distress Score A-J) will be summarized graphically. Plots of mean change from baseline with standard deviation over time, plots of LS mean (from MMRM model) change from baseline with 95% CI over time, and spaghetti plots of individual subject change from baseline over time will be provided for the ITT population only.

A listing for each individual subscale score in NPI will be presented.

## 12. PHARMACOKINETIC ANALYSES

Plasma CT1812 concentrations collected prior to dosing will be summarized for each sampling day with descriptive statistics.

All PK listings, individual and mean pre-dose concentrations, PK tables and figures, and all statistical analyses will be presented using the PK population.

Pharmacokinetic Endpoints:

- CT1812 CSF/plasma concentration ratio (EOS only).
- Predose CT1812 plasma concentrations.

### 12.1 Data Handling

Blood samples will be collected on Days 1, 28, 56, 98, 154, and 182 at the protocol-specified times (within 1.25 hours prior to dosing, i.e., pre-dose samples) for the determination of CT1812 concentrations in plasma.

The raw plasma concentration data will be handled as follows:

**For summary tables and figures for plasma concentrations:**

- For all pre-dose samples, the sampling time will be set to zero.
- Any CT1812 concentration that is reported as below the lower limit of assay quantitation (BLQ) will be set to zero.

### 12.2 Presentation of Plasma Concentrations

**Individual plasma concentration results:**

A raw data listing will be provided displaying the concentration as reported and nominal and actual sampling times relative to the start dose of study drug. Results will be displayed using 3 significant digits.

**Summary statistics of plasma concentrations:**

The plasma concentrations for CT1812 will be summarized by dose group and the nominal time point of the pre-dose samples collected on Days 1, 28, 56, 98, 154, and 182 using descriptive statistics (n, arithmetic mean, SD, coefficient of variation (CV) % of arithmetic mean, median, minimum, maximum, geometric mean, and CV % for the geometric mean).

Results will be displayed using 3 significant digits.

COGNITION Therapeutics  
Protocol number: COG1201

Statistical Analysis Plan  
15 Nov 2024

The CV % for the geometric mean will be calculated using the following formula:

$$CV (\%) = 100 * \sqrt{e^{SD^2} - 1}$$

where SD is of the natural-log transformed data.

### Figures:

An overlay of individual and mean profiles of pre-dose concentrations on Days 1, 28, 56, 98, 154, and 182 will be provided for each dose group on linear scales.

Mean profiles of pre-dose concentrations on Days 1, 28, 56, 98, 154, and 182 will be provided for each dose group on a linear scale and may be presented with or without error bars.

Scatter plots of individual pre-dose concentrations on Days 1, 28, 56, 98, 154, and Day 182 versus BMI, weight, age and gender will be provided for each dose group for both plasma and CSF. Pearson correlation coefficients and p-values will be provided.

### Individual PK Endpoints:

A raw data listing will be provided displaying the individual CT1812 CSF/plasma concentration ratio results will be displayed using 3 significant digits.

### Summary statistics of PK Endpoints:

CT1812 CSF/plasma concentration ratio will be summarized by dosing group using descriptive statistics (n, arithmetic mean, SD, CV% for the arithmetic mean, median, minimum, maximum, geometric mean, and CV% for the geometric mean). Results will be displayed using 3 significant digits.

13. PHARMACODYNAMICS ANALYSES

13.1 Data Handling and Biomarker Measurements

CSF biomarkers: Samples will be collected at screening and Day 182/End of Study.

CSF biomarker being assessed in this study are a-synuclein using **Amprion's** αSyn seed amplification assay (**αS-SAA**)

Plasma biomarkers: Samples will be collected at screening, baseline, Day 28, Day 98, Day 182.

Plasma biomarkers being assessed during this study are as follows: at baseline, Day 98 and Day 182, whereas some biomarkers are being assessed only at screening (V1) (C2N; Precivity AD2)

Biology	Biomarker	Biofluid	Timepoint to be analyzed	Assay Method
Core Biomarker	PrecivityAD2	Plasma	Screening	LC-MS
	pTau181	Plasma	Baseline Day 98 End of the study*	Simoa
	pTau217	Plasma		Simoa
	Aβ42, Aβ40, Aβ42/40 ratio	Plasma		Simoa
Neuroinflammation	GFAP	Plasma		Simoa
Neurodegeneration	NFL	Plasma		Simoa
DLB progression	Total α-Syn	Plasma		IMR
	Phospho-α-Syn	Plasma		IMR
	DDC	Plasma		Simoa

